## 2. ASSESSMENTS

### i. STUDY SCHEDULE

The timing of study is summarized in the Study Schedule.

	Screening	Surgery	Post-Operative Visits	
Visit	1	1	1	2
Month	Pre-op	0	1.5	6
Informed consent	X			
Demographics	X			
Pregnancy	X			
Efficacy				
POPQ	X		X	X
Procedure length		X		
Surgeon+Fellow Satisfaction (VAS)		X		
PGI-I			X	X

PFDI 20	X			
Safety				
Vaginal Wall Appearance (VAS)			X	X
Adverse events		X	X	X
Patient VAS for Pain			X	X

ii. **POP DIAGNOSIS/BASELINE POPQ:** During the preoperative visit for evaluation of POP, the provider (nurse practitioner, resident, fellow, and/or attending) will perform a POPQ exam. Each component, Aa(midline anterior vaginal wall, 3cm above external urethral meatus), Ba(most distal point of the anterior vaginal wall from the vaginal cuff or cervix, C(most distal edge of the cervix or cuff), GH(the distance from the middle of the external urethral meatus to posterior hymen), PB(posterior margin of the genital hiatus to midanal opening), tvl(greatest depth of the vagina, Ap(midline posterior vaginal wall, 3cm proximal to the hymen), Bp(the most distal point of the posterior vaginal wall from the vaginal cuff or cervix), D(posterior fornix) will be assessed. Patient will be diagnosed with POP, defined as the descent of one or more of four different anatomic structures, a) the uterus(cervix), b)the apex of the vagina (in those status post hysterectomy) c) the anterior vaginal wall, or d) the posterior vaginal wall. This is defined on exam as the POPQ points Ba, C, or Bp >0 cm beyond the hymen. In addition, uterine (Cervix) descent into at least the lower half of the vagina (defined as point C>-TVL/2) or post hysterectomy vault into the lower 2/3 of the vagina, Bothersome bulge symptoms as indicated on question 3 of the PFDI-20 form relating to 'sensation of bulging' or 'something falling out,' and desires surgical treatment for uterovaginal or vault prolapse undergoing minimally invasive SCP.

iii. **BASELINE DEMOGRAPHICS:** Patient baseline demographic information will be assessed from the electronic medical record. Information on age, BMI, ethnicity, co-morbidities, and allergies will be obtained.

iv. **INTRAOPERATIVE:** The following will be tracked: intraoperative adverse events, total surgical time, sacrocolpopexy time, mesh attachment time, type of mesh, number of attachment points

(anchor or mesh) including total, anterior, posterior, inability to use randomized technique, conversion to open or alternative technique, surgeon satisfaction with method.

- v. **IMMEDIATE POSTOPERATIVE:** Length of stay in hours, pain medication use will be assessed.
- vi. **POSTOPERATIVE CLINIC VISITS:** In addition to the preoperative visit, patients will have data collection intraoperatively and during postoperative visits at 6 weeks, and 6 months. We will mask patients to the type of attachment used until after their 6 month visit. A provider (not the who did the surgery) will do the postoperative POPQ measurements to ensure masking to the attachment technique used during surgery.
- vii. **SAFETY ASSESSMENTS:** Safety is assessed as a component of the intraoperative record as well as a review of 6 months of electronic medical record of unscheduled office or emergency room visits in addition to assessments at the 6 week and 6 month postoperative visit.

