### 1. OBJECTIVES

1. **PRIMARY OBJECTIVE:** To assess the effect of absorbable anchor compared to suturing for mesh attachment to vagina in robotic assisted sacrocolopexy on the length of surgery for this portion of the procedure.
2. **SECONDARY OBJECTIVES:**
  - i. To assess intraoperative and
  - ii. postoperative complication rates,
  - iii. Intraoperative 10 cm visual analog scale (VAS), to subjectively assess surgeon satisfaction with the technique
  - iv. post-operative Pelvic Organ Prolapse Quantification (POPQ) evaluation for anatomic failure and
  - v. a VAS of the vaginal walls overall appearance
2. **HYPOTHESES** For women undergoing sacrocolpopexy surgery at a large managed care organization:
  1. **PRIMARY HYPOTHESIS:** Attachment of the mesh to the vagina with absorbable anchors compared to standard treatment (suturing) will require 50% shorter surgical time for the mesh attachment portion of the procedure.
  2. **SECONDARY HYPOTHESIS:** Anchor suture staples compared to standard treatment will:
    - i. have similar rates of intra-operative and post-operative complications
    - ii. have similar rates of surgical failure
    - iii. not have different appearance on the VAS of the vaginal walls
    - iv. elicit higher reported satisfaction from surgeons
3. **BACKGROUND**
  1. **PELVIC ORGAN PROLAPSE:** Pelvic organ prolapse (POP) is the descent of one or more of four different anatomic structures: a) the uterus (cervix), b) the apex of the vagina (in those status post-hysterectomy) c) the anterior vaginal wall, or d) the posterior vaginal wall. It is caused by chronic intra-abdominal pressure on weakened pelvic organ supports. An estimated 41.1% of women aged 50-79 have some degree of prolapse on exam [1,2], while only 2.9-8% of all adult women report symptomatic prolapse symptoms [3-5]. Severity of POP is defined by the Pelvic Organ Prolapse Quantification (POPQ) system [6]. Risk factors include age, childbirth (especially vaginal and operative vaginal deliveries), white race, family history, constipation, obesity, smoking, and menopause. Symptoms can include a vaginal bulge, pressure, or discomfort.

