#### **4. OVERVIEW OF DESIGN**

1. **DESIGN DESCRIPTION;** This is a multi-site prospective, randomized, single-blind, 2 arms-parallel, clinical trial to evaluate the effect of absorbable anchor versus suturing of polypropylene mesh to the vaginas fibromuscular layer on the length of procedure for women undergoing SCP for POP. This effect will be studied using timing of the surgical procedure.
2. The study consists of a 1-year enrollment period concurrent with a 1-year single blinded period (the intraoperative data in which the patient is blinded to group assignment, but the surgeon/investigator is not), followed by a 6-month postoperative double blinded period (in which both the patient and surgeon/investigator).
3. During enrollment, patients who meet the inclusion and not the exclusion criteria and provide informed consent for participation will be assigned randomly to receive either absorbable anchor mesh fixation or suture mesh fixation.

Figure 1. Flowchart of study schema

4. **SCREENING PERIOD:** Subject will be screened for eligibility during a 1-year period that will include the preoperative office visit and preoperative unit visit. Office staff (research nurses, nurse practitioners, residents, fellows, attendings) will obtain written informed consent from participants as a part of enrollment. Standard physical exam measures (including POPQ) will be performed during the office visit. The suture allocation sealed envelope will be opened intra-operatively once it is certain the attachment of mesh will occur via a technique that is minimally invasive.
5. **STUDY PERIOD:** Study duration will be the 1 year concurrent period where surgeries are performed as well as the subsequent 6 months where postoperative visits occur. After randomization and surgery occurs subjects will follow up for a total of 6 months, with three visits, one at 6 weeks, one at 6 months. During these postoperative visits, a standard physical exam will be performed looking for signs of POP recurrence, mesh erosion, palpable suture, anchors, and other physical findings. The

patient will complete standardized questionnaires assessing pain, satisfaction and other quality of life indicators.

6. **STUDY POPULATION:** Women with POP, scheduled for minimally invasive SCP will be eligible for enrollment

i. **INCLUSION CRITERIA:** All patients must meet all the following inclusion criteria.

1. Age 21 or older

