2. Diagnosis of POP, defined as the descent of one or more of four different anatomic structures, a)the uterus(cervix), b)the apex of the vagina (in those status post hysterectomy) c) the anterior vaginal wall, or d) the posterior vaginal wall. This is defined on exam as the POPQ points Ba, C, or Bp >0 cm beyond the hymen, uterine(cervix) descent into at least the lower half the vagina (defined as point c> -tv/2) or post hysterectomy vault into the lower 2/3 of the vagina.  
Bothersome bulge symptoms as indicated on question 3 of the Pelvic Floor Disorder Inventory (PFDI-20) form relating to 'sensation of bulging' or something 'falling out'
3. Desire surgical treatment for POP with SCP
4. Available for up to 6 months of follow up
5. Not pregnant or desiring future pregnancy
6. Written informed consent is obtained.

ii. **EXCLUSION CRITERIA;** Patients are ineligible for the study if:

1. Known adverse reaction to synthetic mesh, or complications including but not limited to erosion, fistula, or abscess.
2. Cervical intraepithelial neoplasia (CIN2, CIN3, or cancer)
3. Unresolved chronic pelvic pain
4. Prior abdominal or pelvic radiation
5. Contraindications to the surgical procedures including known horseshoe kidney, pelvic abscess or active diverticular abscess or diverticulitis

7. **METHODS OF RECRUITMENT AND MULTIPLE STRATEGY OF RETENTION:** There are many women in the target population. We will educate the health personnel (research nurses, nurse practitioners residents, fellows, attendings) in two sites of a large managed care organization Female Pelvic Medicine and Reconstructive Surgery (FPMRS) to recruit this population. Subject retention strategies will include a \$20 visa gift card given to the subject on completing the 6 month follow up appointment, as well as phone call reminders of those appointment.

5. **STUDY PROCEDURES**

1. **INTERVENTION:** On day of surgery eligible individuals are randomized to have either absorbable anchor or suture fixation of mesh (Figure 1). The patients and all postoperative study staff will be blinded to treatment assignment and surgical time measurements. A block stratification with a computer-generated randomization schedule will be performed.  
Equipment needed for both techniques will be stocked and readily

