ii. **SECONDARY OUTCOME MEASURE:** Our secondary efficacy objectives include: 1) VAS of the operating surgeon subjective technique satisfaction assessment 2) post-operative POPQ, mesh erosion anatomic assessment, palpable anchor assessment and 3) VAS of the vaginal walls general appearance. The latter two will be recorded by the provider who is blinded at 6 weeks and 6 months, who will perform POP-Q as well as the VAS assessment of the walls of the vagina's general appearance. Surgical failure of a patient is if the points on POP-Q, if  $B_p, B_a \geq 0$  cm, or  $C > - \frac{1}{2}$  TVL. The VAS will have four components, global satisfaction, apex, anterior wall, and posterior wall. The instructions for all four VAS will be as follows: "Please designate a "X" at the VAS that rates closest your sacrocolpopexy evaluation." The anterior compartment assessment at the VAS left side will say "the vaginal mesh at the ANTERIOR seems to lay level without folding or bunching." At the other VAS side the text will say "mesh at the vaginal ANTERIOR is completely folded and bunched." Comparable phrasing will be used on the for posterior and apical compartment VAS. For the global satisfaction VAS, the side on the left it will say "I will use this suture routinely; as it meets my needs for attachment of mesh" and text at the other VAS end will say "I do appreciate the results, I will not use this attachment technique in my practice;"

iii. **SAFETY AND TOXICITY MEASURES:** Safety will be assessed as several points throughout the study. During the admission for surgical care, safety measures and complications will be assessed. During the surgery and admission, complications, including but not limited to hemorrhage, bleeding, nerve injury, infection, urinary retention, bowel injury, bladder/urethral injury will be assessed. Post-operatively at the 6 week, and month visit (along with query of electronic medical record for additional ER and ambulatory visits) additional safety measures will be assessed. At the standardized postoperative visits mesh exposure and erosion will be assessed. In addition pain and reoperation for pain or mesh erosion and exposure will be assessed.

4. **MONITORING AND ETHICAL CONSIDERATIONS:** To safeguard complete, reliable and accurate data, the principal investigator will:
  - i. provide preliminary and follow up training to study coordinators and providers on research procedure, participant recruitment, and completion of outcome reports

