## 6. DATA MANAGEMENT AND ANALYSIS

1. PROCEDURES FOR DATA COLLECTION: Study participants will be closely observed by investigators to make sure that surgical appointments are set up. Data from preoperative period will be taken from the the EMR for the subject. Data for the primary outcome will be abstracted when the subject has their surgery.  
A Clinical report Form (CRF) will be used to collect history, physical examination, operation, operating times, technique, mesh attachment interval times, complications, and subsequent follow-up examination data. The investigators will input data into a pre-formatted spreadsheet. The spreadsheet will be maintained through the Kaiser Permanente San Diego research department on a password protected server and will be audited, reviewed and maintained by the investigators
  - i. Quality of Data: Data of the highest quality will be obtained from management data defined protocols for evaluating its accuracy (using source verification), completeness, accountability, and integrity.
  - ii. Completeness: the investigators will identify and complete any missing data.
  - iii. Accuracy: Errors in data will likely stem from errors in data entry. To minimize this, confirmation of data with a second source and random checks of data, and will be done. Error catching mechanisms in the Excel spread sheet and Access Database will be created with appropriate ranges and limits to help catch mistakes in data entry and allow for more accurate data entry.
  - iv. Auditing: Both sample and schedule-based auditing will be performed. Quarterly audits will be performed with random selection of 10% of the data to verify. Administrative audits will be done on a similar schedule to ensure compliance with Good Clinical Practices of the FDA.
  - v. Accountability: Accountability for data entry and data management will be with the investigators and statistical consultants.
  - vi. Integrity: mirrored hard drives, data back ups and storage on Kaiser Permanente San Diego server, will insure for data integrity.
2. ANALYSIS OF BASELINE DATA: Subject characteristics (measures and demographic information) collected at baseline will be compared across treatment groups, using either chi-square for categorical variables or t-test for continuous variables. We will examine these baseline characteristics for statistically significant differences between treatment groups, and use those that are identified for adjusted analysis correcting for these

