differences in analysis of outcome variables.

3. **STATISTICAL ANALYSIS OF OUTCOMES:** The primary endpoint for this study is the time of completion of mesh attachment. Statistical methods will include t-test or Mann Whitney U test for continuous variables, and chi-squared or Fischer's exact-test for categorical variables. We will collect the primary measure for outcomes of time of mesh attachment as a continuous variable. In addition we will use t-tests to evaluate the mean times of the different attachment approaches. Paired sample t test will be used to evaluate POP-Q values pre and postoperatively. Chi-squared test will be used to examine anatomic failures between the two. We will do risk analysis as appropriate using 95% confidence intervals odds ratios. For the analysis we will use SPSS 22.0.
4. **STUDY POWER AND SAMPLE SIZE:** A time of mesh attachment power calculation was performed using Power and Sample Size program (PS version 3.1.2). If suture mesh attachment interval =  $40 \pm 20$  mins [16,25], a 50% reduction with use of anchors is =  $20\text{mins} \pm 20$  mins. With 80% power and  $\alpha=0.05$ , 17 subjects will be needed for each arm. Anticipating a drop out of up to a 30% we will enroll 25 subjects in each group for a goal of at least 17 participants for each arm.

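### The patient pain VAS has no pre-operative score, so new or worsened pain cannot be identified and a chance imbalance between arms of 17 to 25 can be neither seen nor adjusted for

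*Protocol*

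**What the plan says.** - **Timing.** In the study schedule (Protocol 5.2.i), the row "Patient VAS for Pain" sits in the Safety block. It is marked at the two postoperative visits and is blank at screening and surgery. Protocol 4.5 agrees: it is at the postoperative visits that the "patient will complete standardized questionnaires assessing pain, satisfaction and other quality of life indicators".
- **Role.** Protocol 5.3.iii makes pain a safety measure: "In addition pain and reoperation for pain or mesh erosion and exposure will be assessed".
- **Baseline data.** Protocol 5.2.iii says: "Information on age, BMI, ethnicity, co-morbidities, and allergies will be obtained". The schedule adds POPQ and PFDI-20 before surgery. None of these is a pain score.
- **Pain before surgery.** Protocol 3.1 says of prolapse: "Symptoms can include a vaginal bulge, pressure, or discomfort". The only exclusion that bears on this (Protocol 4.6.ii) is "Unresolved chronic pelvic pain".
- **Analysis.** Protocol 6.2 and SAP 1.2 test baseline characteristics for differences between arms and "use those that are identified for adjusted analysis correcting for these" differences. No analysis specific to pain is stated, so the general rule of t-test or Mann-Whitney for continuous variables applies. POPQ is measured before and after surgery and has its own pre/post analysis: "Paired sample t test will be used to evaluate POP-Q values pre and postoperatively".

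**The concern.** A pain score taken only after surgery mixes two things: pain that follows the fixation, and discomfort the woman already had. The Protocol itself says prolapse can cause discomfort, and the exclusion removes only unresolved chronic pelvic pain, so baseline scores are unlikely to be zero in every woman. Three things are lost.

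1. In an individual woman, unchanged discomfort cannot be separated from new or worsened pain, so the level of pain in either arm is hard to interpret.
2. Between the arms, a chance difference in baseline pain goes unseen. The plan's adjustment rule works only on characteristics collected at baseline, so it cannot reach pain.
3. Variation between women that a baseline score would explain stays in the error term and widens the interval. The secondary hypothesis is that complication rates are similar. Under a claim of similarity, avoidable noise makes a real difference easier to miss.

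A pre-operative score cannot be recovered once surgery has taken place.

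**Working it through.** **The plan's sample size (Protocol 6.4, SAP 1.4).** Inputs: 40 versus 20 minutes, SD 20, 80% power, alpha 0.05 (sidedness not stated; two-sided reproduces the figure).

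- Normal approximation: n = 2 × (1.96 + 0.84)² × (20/20)² = 15.7, so 16 per arm.
- Two-sample t-test: 16.7, so 17 per arm, as stated.
- After 30% dropout: 17 / 0.70 = 24.3, so 25 per arm, 50 in total, as stated.

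The pain comparison will therefore rest on 17 to 25 women per arm. The number itself is set by mesh attachment time and does not depend on the pain VAS.

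**Chance imbalance and the gain from adjustment.** The correlation r between pre-operative and follow-up pain VAS is not in the documents. I assume 0.3 to 0.6.

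- SD of the chance difference in baseline means, in baseline-SD units: √(2/n).
- Part of that carried into the follow-up comparison, in follow-up SD units: r × √(2/n).
- Variance factor under ANCOVA: 1 − r², which is 0.91, 0.75 and 0.64 at r = 0.3, 0.5 and 0.6.
- Detectable difference (two-sided 0.05, 80% power): the unadjusted value times √(1 − r²).

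| Quantity | 25 per arm | 17 per arm |
|---|---|---|
| SD of chance baseline difference | √(2/25) = 0.28 | √(2/17) = 0.34 |
| 95% range (1.96 × SD) | ±0.55 | ±0.67 |
| Chance that it exceeds 0.25 SD | 38% | 47% |
| Carried to follow-up, r = 0.3 to 0.6 | 0.08 to 0.17 | 0.10 to 0.21 |
| Detectable difference, unadjusted | 0.81 SD | 0.99 SD |
| Detectable difference, adjusted, r = 0.3 / 0.5 / 0.6 | 0.77 / 0.70 / 0.65 SD | 0.95 / 0.86 / 0.79 SD |

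The variance of the arm difference falls by 9%, 25% and 36% at r = 0.3, 0.5 and 0.6. Estimating the slope takes a little back. For a normally distributed covariate the expected inflation is 1 + 1/(2n − 4), which is 1 + 1/46 = 1.022 at 25 per arm and 1 + 1/30 = 1.033 at 17.

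- At 25 per arm, the net reduction runs from 1 − 0.91 × 1.022 = 7% to 1 − 0.64 × 1.022 = 35%.
- At 17 per arm, it runs from 1 − 0.91 × 1.033 = 6% to 1 − 0.64 × 1.033 = 34%.

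**Validity as a covariate.** Randomisation is on the day of surgery (Protocol 5.1), and the envelope is opened during the operation (Protocol 4.4). A score taken at screening therefore precedes allocation.

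**The case against.** A fair opponent would say that a postoperative safety score compared between randomised arms is valid without a baseline.

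- **No bias.** A reader might infer that pre-existing pain is held against the anchor technique. The documents do not support that. Allocation is random and patients are blinded, so such pain falls on both arms alike in expectation. The unadjusted standard error already includes the chance imbalance. This stands.
- **The background.** A reader might also take pain to be the specific warning that the Protocol raises for these anchors. Protocol 3.3 is mixed: in hernia repair it reports less postoperative pain with anchoring than with suture, and it links longer-term pain to non-absorbable anchors. This trial uses absorbable ones, for which the concern named there is recurrence. This stands too.
- **The size.** The 0.28 and 0.34 SD figures describe baseline pain, not the outcome. What reaches follow-up is smaller by the factor r. A low r is plausible: the exclusion narrows the baseline range, and surgery corrects the prolapse behind some of the discomfort. At r = 0.3 the interval narrows by only about 5% (√0.91 = 0.954), and the comparison can detect only large differences with or without adjustment.
- **Substitutes and rank.** PFDI-20, co-morbidities and history allow crude adjustment, and reoperation for pain needs no baseline. Pain is in no numbered objective or hypothesis and is not among the listed secondary outcome measures.

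All of this limits the weight of the point but does not remove it. Randomisation balances the arms on average, but it does not show whether a given woman's pain is new. Crude substitutes are not a score on the same scale.

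**Conclusion.** The point holds as a gap in precision and interpretability for a safety measure. Neither document plans a pre-operative pain score, so neither new pain nor change in pain can be derived, and the plan's adjustment rule cannot take pain into account. The chance imbalance that reaches the follow-up comparison has an SD of about 0.08 to 0.21 SD, and adjustment would reduce the variance of the arm difference by about 9% to 36% (6% to 35% net of estimating the slope). Both ranges rest on the assumed correlation of 0.3 to 0.6. The imbalance is centred on zero, so no bias against either technique follows. Mesh attachment time and its sample size are untouched. The case for acting is that the remedy is cheap and the missing score cannot be collected later.

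**What to change.** 1. In the study schedule (Protocol 5.2.i), add an X for the patient pain VAS in the Screening column, completed with the PFDI-20 and before randomisation. Add pain to the baseline data in Protocol 5.2.iii.
2. In Protocol 6.3 and SAP 1.3, pre-specify that the arms are compared on the 6-week and 6-month pain VAS by ANCOVA adjusted for the baseline score. Name the covariate in advance. If it were left to the rule in Protocol 6.2 and SAP 1.2, it would be used only when the arms happened to differ significantly at baseline, and most of the precision gain would be lost.
3. Report change from baseline alongside the raw scores in each arm.
4. Leave adverse-event and complication counting as planned. The baseline score adds information to those counts and should not be used to remove events from them.

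The cost is about a minute of each woman's time at a visit that already includes a questionnaire, and one covariate in the model. Women enrolled before the change will have no baseline score, and the report should give their number by arm.
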